#### **11.5.1.3 Non-Measurable Lesions**

All other lesions, including small lesions (longest diameter <20 mm with conventional techniques or <10 mm with spiral CT scan), i.e., bone lesions, ascites, pleural/pericardial effusion, cystic lesions, and abdominal masses that are not confirmed and followed by imaging techniques.

All measurements should be taken and recorded in metric notation, using a ruler or calipers. All baseline evaluations should be performed as closely as possible to the beginning of treatment, preferably within two weeks of treatment initiation, and never more than 4 weeks before the beginning of the treatment.

The same method of assessment and the same technique should be used to characterize each identified and reported lesion at baseline and during follow up.

### **11.5.2 Methods of Measurements**

CT and MRI are the best currently available and reproducible methods to measure target lesions selected for response assessment. Conventional CT and MRI should be performed with cuts of 10 mm or less in slice thickness contiguously. Spiral CT should be performed using a 5 mm contiguous reconstruction algorithm. This applies to tumors of the chest, abdomen and pelvis. Head and neck tumors and those of extremities usually require specific protocols.

### **11.5.3 Response Criteria**

#### **11.5.3.1 Evaluation of Target Lesions by RECIST 1.1**

- **Complete Response (CR):** Disappearance of the target lesion
- **Partial Response (PR):** At least a 30% decrease in the sum of the LD of target lesions, taking as reference the baseline sum LD
- **Progressive Disease (PD):** At least a 20% increase in the sum of the LD of target lesion, or the appearance of one or more new lesions
- **Stable Disease (SD):** Neither sufficient shrinkage to qualify for PR nor sufficient increase to qualify for PD, taking as reference the smallest sum LD since the treatment started

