Endpoints:	
Phase I:
 
 
• Safety profile of BMS-986205 in combination with nivolumab in unresectable HCC using CTCAE V5.0 criteria
 
 
Phase II:
 
 
• Safety profile of BMS-986205 in combination with nivolumab in unresectable HCC using CTCAE V5.0 criteria
 
• ORR of BMS-986205 in combination with nivolumab in unresectable HCC using RECIST 1.1 criteria.
 
 
Secondary Endpoints
 
 
• DCR which include CR, PR and SD from the first report of SD or better until progression by RECIST 1.1
 
• DOR defined by the first report of SD or better until progression by RECIST 1.1
 
• ORR using immune RECIST (iRECIST)
 
• PFS defined by date of enrollment until the first date of documented disease progression or death by RECIST 1.1
 
• OS defined by date of enrollment until death from any cause by RECIST 1.1.
 
• Correlation of PD-1/L1 expression (+/-) and IDO1 expression (+/-) at: 1) baseline, 2) on treatment, and 3) progression, with ORR, PFS and OS.
 

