### **11.5.1 Disease Parameters**

#### **11.5.1.1 Measurable Disease**

The presence of at least one measurable lesion. If the measurable disease is restricted to a solitary lesion, its neoplastic nature should be confirmed by cytology/histology.

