#### **11.5.1.2 Measurable Lesions**

Lesions that can be accurately measured in at least one dimension with longest diameter 20mm using conventional techniques or 10mm with spiral CT scan.

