### 11.5.3.2 Evaluation of Best Overall Response

The best overall response is the best response recorded from the start of the treatment until disease progression/recurrence (taking as reference for PD the smallest measurements recorded since the treatment started). In general, the patient's best response assignment will depend on the achievement of both measurement and confirmation criteria.

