#### **11.5.3.4 Duration of Overall Response**

The duration of overall response is measured from the time measurement criteria are met for CR or PR (whichever status is recorded first) until the first date that recurrence or PD is objectively documented, taking as reference for PD the smallest measurements recorded since the treatment started.

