## Appendix 12: Immune RECIST Criteria

	RECIST 1.1	iRECIST
Definitions of measurable and non-measurable disease; numbers and site of target disease	Measurable lesions are $\geq 10$ mm in diameter ( $\geq 15$ mm for nodal lesions); maximum of five lesions (two per organ); all other disease is considered non-target (must be $\geq 10$ mm in short axis for nodal disease)	No change from RECIST 1.1; however, new lesions are assessed as per RECIST 1.1 but are recorded separately on the case report form (but not included in the sum of lesions for target lesions identified at baseline)
Complete response, partial response, or stable disease	Cannot have met criteria for progression before complete response, partial response, or stable disease	Can have had iUPD (one or more instances), but not iCPD, before iCR, iPR, or iSD
Confirmation of complete response or partial response	Only required for non-randomised trials	As per RECIST 1.1
Confirmation of stable disease	Not required	As per RECIST 1.1
New lesions	Result in progression; recorded but not measured	Results in iUPD but iCPD is only assigned on the basis of this category if at next assessment additional new lesions appear or an increase in size of new lesions is seen ( $\geq 5$ mm for sum of new lesion target or any increase in new lesion non-target); the appearance of new lesions when none have previously been recorded, can also confirm iCPD
Independent blinded review and central collection of scans	Recommended in some circumstances—eg, in some trials with progression-based endpoints planned for marketing approval	Collection of scans (but not independent review) recommended for all trials
Confirmation of progression	Not required (unless equivocal)	Required
Consideration of clinical status	Not included in assessment	Clinical stability is considered when deciding whether treatment is continued after iUPD

"i" indicates immune responses assigned using iRECIST. RECIST=Response Evaluation Criteria in Solid Tumours. iUPD=unconfirmed progression. iCPD=confirmed progression. iCR=complete response. iPR=partial response. iSD=stable disease.

Table 1: Comparison of RECIST 1.1 and iRECIST

	Timepoint response with no previous iUPD in any category	Timepoint response with previous iUPD in any category*
Target lesions: iCR; non-target lesions: iCR; new lesions: no	iCR	iCR
Target lesions: iCR; non-target lesions: non-iCR/non-iUPD; new lesions: no	iPR	iPR

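### Section 11.5.3.1 sets target-lesion PD at a 20% rise over the nadir with no minimum change in mm, so for small target sums a 2 to 4 mm reading difference can end PFS or DOR.

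*Combined protocol and SAP*

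**What the plan says.** Under a heading that names RECIST 1.1, section 11.5.3.1 gives target-lesion PD as "At least a 20% increase in the sum of the LD of target lesion, or the appearance of one or more new lesions". The bullet does not state the reference. Section 11.5.3.2 supplies it: "taking as reference for PD the smallest measurements recorded since the treatment started". Section 11.5.3.4 repeats it for duration of response.

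The entry rules allow small sums. Section 11.5.1.1 asks for "The presence of at least one measurable lesion", and section 11.5.1.2 accepts a "longest diameter 20mm using conventional techniques or 10mm with spiral CT scan". On imaging, section 11.5.2 says "Spiral CT should be performed using a 5 mm contiguous reconstruction algorithm".

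The PD date feeds two time-to-event endpoints. The synopsis (Endpoints) has "PFS defined by date of enrollment until the first date of documented disease progression or death by RECIST 1.1". Section 11.5.3.4 runs DOR "until the first date that recurrence or PD is objectively documented". For response, the RECIST 1.1 column of Appendix 12 reads "Cannot have met criteria for progression before complete response, partial response, or stable disease".

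Three places deal with confirming PD, and they do not agree:
- Section 11.5.3.3 asks for confirmation of all PD but points to a section 6.2 that does not exist.
- Section 6.1.1 requires confirmation at least 4 weeks later for treatment decisions under iRECIST. It refers to Table 2, which has no mm criterion.
- Appendix 12 says RECIST 1.1 progression needs no confirmation unless it is equivocal.

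The only mm floor on growth of the target sum is the 5 mm in the iRECIST table of Appendix 12, where it serves to confirm iCPD.

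**The concern.** A purely relative threshold measured from the nadir asks for fewer mm as the tumour shrinks. At a small sum, the rise that counts as progression is of the same order as plausible reading variation. The reference is also the lowest of several noisy readings, so it drifts downward over time even when nothing changes.

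PFS is at risk in patients with a small baseline sum. DOR is at risk in responders with a small nadir. For example, a responder read at 40 mm, then 12 mm, then 15 mm has risen by 3/12 = 25% and is in PD, although the sum is still 1 - 15/40 = 62.5% below baseline. In a cohort of 17, a few such dates can move a Kaplan-Meier median.

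**Working it through.** **Plan's own figure.** The documents give no figure for this rule. The only calculation tied to response is the Simon design in sections 14.1 and 14.2: at least 1 of 9, then at least 3 of 17. Exact enumeration gives 81.2% power at 25% and a type I error of 4.66% at 5%, so the stated 80% and 0.05 reproduce. Nothing below disputes them.

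**Inputs.** From the protocol: the 20% threshold (11.5.3.1), the nadir reference (11.5.3.2, 11.5.3.4), a minimum sum of 10 mm on spiral CT (11.5.1.1, 11.5.1.2), and scans at weeks 8 and 16 and then every 12 weeks (11.5). Five scans therefore run to week 52. Assumed: a reading error SD of 1 mm per sum, range 0.75 to 1.5 mm.

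**Step 1: rise needed, 0.20 x reference sum.**

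| Reference sum | Rise for PD |
|---|---|
| 10 mm | 2.0 mm |
| 12 mm | 2.4 mm |
| 15 mm | 3.0 mm |
| 20 mm | 4.0 mm |
| 25 mm | 5.0 mm |
| 50 mm | 10.0 mm |

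A 5 mm floor binds only below 25 mm. For a patient in PR (at least a 30% fall), a nadir just under 25 mm at exactly -30% means a baseline of 25/0.7 = 35.7 mm. Deeper responses from larger baselines can also fall below 25 mm.

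**Step 2: one nadir reading, one later reading, no true change.** With true sum T and error SD s, P(false PD) = 1 - Phi[0.2T / (s x sqrt(1 + 1.2^2))].
- T = 10, s = 1: 2/1.562 = 1.28, giving 10%.
- T = 15, s = 1: 3/1.562 = 1.92, giving just under 3%.
- T = 10, s = 1, with a 5 mm floor: 5/1.414 = 3.54, giving 0.02%.

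Simulation of the same two-reading case gives 10.0%, 2.8% and 0.02%.

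**Step 3: five scans.** Simulated with a constant true sum and readings rounded to 1 mm. PD is called when a reading is at least 1.2 times the smallest so far. Brackets show SD 0.75 to 1.5 mm.

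| True sum | One reading suffices | Next scan must confirm (SD 1 mm) | 5 mm floor, no confirmation |
|---|---|---|---|
| 10 mm | 74% (55-89%) | 30% | about 1% (0-17%) |
| 15 mm | 33% (11-67%) | 7% | about 1% (0-17%) |
| 20 mm | 8% (1-39%) | 1% | about 1% (0-17%) |

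The confirmation column needs both readings within the five scans. If a rise at the fifth scan may be confirmed at a sixth, it becomes 38%, 9% and 1%. Confirmation does not remove the problem because an under-read nadir stays the reference. After only two scans at 10 mm, the single-reading rule gives 33%, against 0.3% with the floor.

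**Step 4: ORR.** A response is lost only if a false rise comes before the shrinkage. With an SD of 1 mm, a flat first scan followed by a 40% fall is lost in 15% of cases at a 10 mm baseline, 4% at 15 mm and 0.7% at 20 mm. A gradual responder (-15%, then -40%) is lost in 2% at 10 mm and under 0.1% at 15 mm.

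**The case against.** **The citation governs.** Section 11.5 says response and progression are evaluated by the RECIST 1.1 guideline, and 11.5.3.1 may be only a short summary of it. This stands in part. A reader who applies the guideline itself may use a different rule, but its full PD text is not in the documents and I do not rely on it. The printed rule is the one at hand, and two readers could date PD differently.

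**PD must be confirmed.** Section 11.5.3.3 says so, and Appendix 12 leaves room for confirming equivocal progression. This also stands in part: confirmation cuts the false rate by more than half at 10 mm and by more at 15 and 20 mm. But the cross-reference is broken, and Appendix 12 does not generally require confirmation under RECIST 1.1.

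**Few patients, modest stakes.** The largest rates need a total target sum of 10 mm and a year of scans without change. The population has unresectable or metastatic disease with a lesion suitable for core biopsy, and up to five lesions may be summed. PFS and DOR are descriptive, with no decision rule. All of this stands and limits the weight of the point.

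**The 5 mm figure has another purpose.** In Appendix 12 it marks a further increase after iUPD. That is fair: the documents offer it as a precedent for target-sum growth and do not establish it for RECIST 1.1 PD.

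**Stronger readings.** A reader might infer that noise-driven PD undermines the 3-of-17 decision. The documents do not support this: well-shrunk responders have already recorded PR, which best response under 11.5.3.2 keeps, and step 4 leaves only a narrow group. A reader might also infer that patients would stop treatment on a 2 mm change. Section 6.0 ties stopping for progression to confirmed iRECIST progression, which is a separate assessment.

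**Conclusion.** The point holds for PFS and DOR in patients whose baseline or nadir target sum is below 25 mm. Applied as printed, the rule makes PD sensitive to 2 to 4 mm. Whether one reading suffices is unclear because the confirmation text conflicts, so the honest range at a 10 mm sum runs from about 30% (confirmed) to about 74% (single reading) over five scans at an SD of 1 mm. At 20 mm it runs from about 1% to 8%.

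These figures assume no true change, independent normal reading errors and the stated SD. With an SD of 1.5 mm, even the 5 mm floor leaves about 17%, so the floor reduces the problem without abolishing it. The documents give neither baseline sums nor reading error, so the share of the 17 patients affected is unknown and could be small. The effect on ORR is minor. The change is worth making because it is nearly free, not because the main conclusion depends on it.

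**What to change.** In section 11.5.3.1, state target-lesion PD as at least a 20% increase over the smallest sum on study and an absolute increase of at least 5 mm, or the appearance of new lesions. Say that this definition dates RECIST 1.1 endpoints: PFS, DOR and best response.

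Reconcile sections 6.1.1 and 11.5.3.3 and Appendix 12 on whether RECIST 1.1 PD needs confirmation for endpoint purposes and, if it does, which date counts. Correct the reference to section 6.2.

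The cost is a few sentences, with no extra patients; the floor itself needs no extra scans. The one downside is that true slow growth in sums under 25 mm may be dated about one scan later. Treatment decisions under iRECIST are not changed by this.

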### 11.5.3.2 Evaluation of Best Overall Response

The best overall response is the best response recorded from the start of the treatment until disease progression/recurrence (taking as reference for PD the smallest measurements recorded since the treatment started). In general, the patient's best response assignment will depend on the achievement of both measurement and confirmation criteria.

**Table 2. Best Overall Response Evaluation**

Best Overall Response Evaluation		
Target Lesion	New Lesion	Overall Response
CR	No	CR
PR	No	PR
SD	No	SD
PD	Yes or No	PD

Patients with a global deterioration of health status requiring discontinuation of treatment without objective evidence of disease progression at that time should be classified as having "symptomatic deterioration". Every effort should be made to document the objective progression even after discontinuation of treatment.

In some circumstances it may be difficult to distinguish residual disease from normal tissue.

When the evaluation of complete response depends on this determination, it is recommended that the residual lesion be investigated (fine needle aspirate/biopsy) to confirm the complete response status.

### 11.5.3.3 Confirmation

The main goal of confirmation of objective response is to avoid overestimating the response rate observed. For reporting the study outcomes the response rate and confirmed response rate will be made clear. For interval evaluation of response rates during the Simon-two stage study responses do not need to be confirmed for the study to progress. To be assigned the status of confirmed responses must be confirmed by repeat assessments that should be performed no less than 4 weeks after the criteria for response are first met. Longer intervals as determined by the study protocol may also be appropriate. In the case of SD, follow-up measurements must have met the SD criteria at least once after study entry at a minimum interval (in general, not less than 6-8 weeks) that is defined in the study protocol. For PD all results should be confirmed as described in section 6.2.

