### 6.1 Discontinuation Criteria

#### 6.1.1 Discontinuation Due to Disease Progression

Immunotherapeutic agents such as BMS-986205 and nivolumab may produce antitumor effects by potentiating endogenous cancer-specific immune responses. The response patterns seen with such an approach may extend beyond the typical time course of responses seen with cytotoxic agents and can manifest as a clinical response after an initial increase in tumor burden or even the appearance of new lesions.

Immune RECIST will be used for assessment of tumor response for the purposes of managing subjects on study treatment and decision-making for discontinuation of study therapy due to disease progression. PD should be confirmed no earlier than 4 weeks later according to the criteria outlined in Table 2. Subjects who are deemed clinically unstable or who have biopsy proven new metastatic lesions are not required to have repeat imaging for confirmation. This decision will be based on the Investigator's clinical judgment of a subject's overall clinical condition, including performance status, clinical symptoms, and laboratory data. At a minimum, subjects must meet the below criteria for continued treatment on study after disease progression is identified at a tumor assessment.

When feasible, subjects should not be discontinued until progression is confirmed; however, the decision to continue study treatment after the first evidence of disease progression is at the Investigator's discretion based on the clinical status of the subject.

Subjects may receive study treatment while waiting for confirmation of PD if they are clinically stable as defined by the following criteria:

- No decline in ECOG performance status.
- Absence of new or worsening symptoms.
- Absence of rapid progression of disease.
- Absence of progressive tumor at critical anatomical sites (e.g., spinal cord compression) requiring urgent alternative medical intervention.

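### Section 11.5.3.3 asks for confirmation of all progression without limiting this to iRECIST, which conflicts with the RECIST 1.1 rules in Appendix 12 and leaves the primary ORR open to two readings

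*Combined protocol and SAP*

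**What the plan says.** The primary efficacy endpoint in the Protocol Synopsis is "ORR of BMS-986205 in combination with nivolumab in unresectable HCC using RECIST 1.1 criteria"; ORR by iRECIST is a separate secondary endpoint. Section 11.5 applies both criteria sets, and Section 11.5.3.1 gives the RECIST 1.1 target-lesion definitions.

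Section 11.5.3.2 sets the response window: "The best overall response is the best response recorded from the start of the treatment until disease progression/recurrence". It does not say whether this means first or confirmed progression, and it adds that the assignment will in general depend on confirmation as well as measurement. The next subsection, on confirmation, ends with "For PD all results should be confirmed as described in section 6.2".

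The contents list goes from Section 6.1 to Section 7.0, so there is no Section 6.2. The only procedure for confirming progression is in Section 6.1.1: "PD should be confirmed no earlier than 4 weeks later according to the criteria outlined in Table 2". That section uses iRECIST to manage patients on treatment and to decide on discontinuation.

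The time-to-event definitions use first documentation. The Synopsis has "PFS defined by date of enrollment until the first date of documented disease progression or death by RECIST 1.1". Section 11.5.3.4 runs DOR "until the first date that recurrence or PD is objectively documented".

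Appendix 12 sets the two systems side by side. For RECIST 1.1, confirmation of progression is not needed unless it is equivocal; for iRECIST it is required. On response, the RECIST 1.1 column reads "Cannot have met criteria for progression before complete response, partial response, or stable disease".

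**The concern.** One sentence carries an iRECIST requirement into a section that also governs the RECIST 1.1 endpoints. An assessor who follows it could treat a first RECIST 1.1 progression as provisional. If the next scan then shows shrinkage, the patient might be recorded as a RECIST 1.1 responder. That response belongs under iRECIST, which is the secondary endpoint.

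Such patients are foreseeable. Section 6.1.1 anticipates responses after an initial increase in tumor burden and lets clinically stable patients stay on treatment while progression is being confirmed, so post-progression scans on treatment will exist.

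The decision rules turn on very few patients: at least 1 response in 9 to continue, and at least 3 in 17 to call the treatment worthy of further study. One patient classified differently can change either decision. Section 11.5.3.3 also lets unconfirmed responses count at the interim look.

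**Working it through.** **1. Setting the texts side by side**

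- *Must progression be confirmed?* Section 11.5.3.3: yes, all of it. Appendix 12, RECIST 1.1: no, unless equivocal. Appendix 12, iRECIST: yes. The sentence therefore matches the iRECIST column and contradicts the RECIST 1.1 column.
- *Can a response follow progression?* Appendix 12, RECIST 1.1: no. Table 2 agrees, mapping target-lesion PD to overall PD with no confirmation step. Section 11.5.3.2 stops at progression but does not say which progression.
- *Which date counts?* PFS (Synopsis) and DOR (Section 11.5.3.4): first documentation. Section 11.5.3.3 gives no date rule.
- *Where is confirmation described?* Section 6.2 does not exist. Section 6.1.1 concerns treatment decisions and refers to Table 2, which contains no confirmation criteria.

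**2. Reproducing the design**

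Inputs from Sections 14.1 and 14.2: n1 = 9, continue with at least 1 response; N = 17, success with at least 3; p0 = 5%, p1 = 25%, one-sided alpha 0.05, power 80%. The Study Schema prints a different parameter set (n1 = 16, total 30), which is not used here.

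P(success | p) = Σ over x = 1 to 9 of P(X1 = x) × P(X2 ≥ 3 − x), with X1 ~ Bin(9, p) and X2 ~ Bin(8, p).

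At p = 0.05:
- P(X1 = 0) = 0.95^9 = 0.6302, the early-stopping probability
- P(X1 = 1) = 0.2985 and P(X2 ≥ 2) = 0.0573; product 0.0171
- P(X1 = 2) = 0.0629 and P(X2 ≥ 1) = 0.3366; product 0.0212
- P(X1 ≥ 3) = 0.0084
- Sum: 0.0466 after rounding

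At p = 0.25 the same formula gives 0.812. A search over designs up to N = 40 returns this one as the Simon optimal design, with expected N 11.96 under p0. The stated design reproduces.

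**3. Illustration of sensitivity**

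Suppose the true RECIST 1.1 rate is 5% and counting post-progression responses adds d percentage points. The documents give no value for d, so it is an assumption. Putting p = 0.05 + d into the formula:

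| d (points) | Pass stage 1 | Declare success |
|---|---|---|
| 0 | 0.370 | 0.047 |
| 1 | 0.427 | 0.073 |
| 2 | 0.480 | 0.104 |
| 3 | 0.528 | 0.140 |
| 5 | 0.613 | 0.223 |

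These are the rejection probabilities of the same design at a higher rate. They show how sensitive the rule is. They do not show that the wording causes such a shift.

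**4. Dates**

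If progression were dated at the confirming scan, PFS and DOR would end at least 4 weeks later (Section 6.1.1). On scheduled scans alone (weeks 8 and 16, then every 12 weeks) the shift would be 16 − 8 = 8 weeks for progression at week 8, or 12 weeks from week 16 onwards, before the 7-day windows. No text sets the date at the confirming scan.

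**The case against.** The strongest reply is that the documents already supply the RECIST 1.1 rule and the sentence is a loose pointer to the iRECIST procedure. Section 11.5 covers both systems. The only confirmation procedure, Section 6.1.1, is an iRECIST rule for treatment decisions; it exempts clinically unstable patients and those with biopsy-proven new metastases, and asks for confirmation before discontinuation only where feasible. On this view the sentence brings that narrower scope with it.

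Much of this stands, and it rules out three stronger readings that a reader might infer:

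- *That the plan lets responses after progression count in the primary ORR.* No text says so. Appendix 12 bars it for RECIST 1.1, and Table 2 maps progression to progression.
- *That PFS and DOR are lengthened.* Progression can be confirmed later and still be dated at the first scan, and both definitions use first documentation.
- *That the primary analysis as a whole is compromised.* Only ORR is primary among the efficacy endpoints. PFS and DOR are secondary in Section 2.2, and exploratory in Section 3.0.

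The reply does not remove the conflict. The sentence is unqualified, its reference leads nowhere, and Section 11.5.3.2 makes best response depend on confirmation just before the sentence calls for all progression to be confirmed. An assessor has to choose between the body text and an appendix table.

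**Conclusion.** The conflict is real but limited. Read literally, Section 11.5.3.3 contradicts the RECIST 1.1 column of Appendix 12 and fits poorly with the first-documentation dates for PFS and DOR. With Section 11.5.3.2 it permits, without stating, a reading that would blur the primary RECIST 1.1 ORR with the secondary iRECIST ORR.

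N = 17, the attained alpha of 0.0466 and the power of 0.812 are unaffected. The effect on the trial's decision cannot be estimated from the documents. The rise from 0.047 to 0.073 for one added percentage point is an illustration resting wholly on that assumed point. What can be said firmly is that one patient classified differently could change either decision. The rule should therefore be settled before responses are read.

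**What to change.** Amend Section 11.5.3.3 so that:

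- the confirmation sentence applies only to iRECIST assessments (iUPD to iCPD) and refers to Section 6.1.1;
- for RECIST 1.1 ORR, DCR, DOR and PFS, the first unequivocal documented progression is the event and its date is the event date;
- equivocal progression is handled as in Appendix 12. A rule that simply made the first progression final would drop that exception and create a new conflict;
- shrinkage after RECIST 1.1 progression counts only under iRECIST.

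The reference from Section 6.1.1 to Table 2 should be checked at the same time, since that table has no confirmation criteria. The iRECIST rule for treatment decisions in Section 6.1.1 stays as it is.

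The cost is a short wording amendment: no new data, no added scans, and no change to sample size or decision rules.
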